1.1 Study design

SEARCH-Youth is an implementation science study, designed to rigorously evaluate the effects of a combination intervention, including life-stage assessments, structured choice clinic access, and rapid viral load feedback, on care outcomes among adolescents and young adults (15-24 years) with HIV. Since the personalized intervention is delivered through changes in clinical practice, the unit of randomization is government sponsored health clinics in rural western Kenya and southwestern Uganda. Specifically, a total of 28 clinics (14 per country) were randomized to the SEARCH-Youth intervention or the optimized standard of care: differentiated ART care, standard clinic hours, routine viral load monitoring, and access to 2nd and 3rd line ART. To improve statistical power, randomization occurred within strata defined by country, clinic size, and prior participation in the SEARCH Study (ClinicalTrials.gov: NCT01864603). Formal power calculations are given in the Appendix.

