Effect estimation: Viral suppression at two-years will be compared between randomized arms using *Two-Stage TMLE*, an approach that appropriately accounts for the dependence of outcomes within clusters [2]. In the first stage, viral suppression will be estimated for each clinic, as described above. In the second stage, we will use a cluster-level TMLE to evaluate intervention effectiveness by comparing the clinic-specific endpoints between randomized arms, adaptively selecting the clinic-level adjustment variables that optimize precision, while tightly preserving Type-I error control [2, 4, 5]. Specifically, we will use leave-one-out cross-validation to select from the following baseline covariates the combination that maximizes empirical efficiency: the clinic-specific number of adolescents and young adults in HIV care at baseline, the clinic-specific proportion with viral suppression among those engaged at baseline, or nothing (unadjusted). In secondary analyses, we will implement an unadjusted effect estimator as the contrast in the average proportion with viral suppression between arms.

The primary effect will be on the relative scale for the N=28 clinics in the trial (i.e., the sample

risk ratio) [6-10]:

$$\frac{\psi(1)}{\psi(0)} = \frac{1/N \sum_{i=1}^N \alpha_i Y_i(1)}{1/N \sum_{i=1}^N \alpha_i Y_i(0)}$$

where α_i are weights for the clinic i ; $Y_i(1)$ is the counterfactual proportion with viral suppression at 2 years if possibly contrary-to-fact clinic i were in the intervention arm ($Z = 1$), and $Y_i(0)$ is the counterfactual proportion with viral suppression at 2 years if possibly contrary-to-fact clinic i were in the standard-of-care arm ($Z = 0$). In secondary analyses, we will examine the effect on the absolute scale: $\psi(1) - \psi(0)$. Primary analyses will weight the N clinics equally: $\alpha_i = 1$ for all i . In sensitivity analyses (described below), we will weight according to the number of participants included in the analysis [5].

Statistical inference: In all analyses, we will use the influence curve for standard error estimation [2, 10]. All analyses will use the Student's t -distribution with $28-2=26$ degrees of freedom as finite sample approximation to the standard normal distribution [11].

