2.1 Sensitivity analyses

In addition to the previously described sensitivity analyses, we will evaluate the intervention effect using a *Single-Stage TMLE* that pools across clinics to estimate and compare the average of individual-level outcomes between arms [2, 5, 12]. This approach naturally estimates an individual-level effect (e.g., the by-arm contrast in the overall proportion with viral suppression) and thus weights participants, not clinics, equally. As detailed in [5], however, this effect can equivalently be estimated with Two-Stage TMLE when the appropriate weights are applied. The single-stage approach is preferable when the cluster size is small or the outcome is rare. (The two-stage approach is preferable when the outcome is subject to differential measurement or censoring.)

In sensitivity analyses of the primary endpoint evaluated with the Single-Stage TMLE, we will adaptively select from the following prespecified set the combination of baseline variables that maximizes empirical efficiency: age, sex, viral suppression status, or nothing (unadjusted). In sensitivity analyses of secondary endpoints adjusting for potentially differential measurement of viral loads, we will include these variables as well as the post-baseline variable of outmigration in the adjustment set in a longitudinal TMLE [13, 14]. Throughout statistical inference will account for clustering through influence curve-based estimation, described above.

As an additional sensitivity analysis, we may define viral suppression as HIV RNA<50 cps/mL.

Finally, given existing programs to support adherence and retention among adolescents and young adults with HIV in study clinics, we may conduct sensitivity analyses to exclude these clinics. We

note both intervention and control participants had full access to these programs; the intervention was added to, not in place of, the standard-of-care.

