2.2 Subgroups

To understand effect heterogeneity, we will repeat the above analyses within the following pre-specified baseline subgroups: country, sex, age group (15-19 years; 20-24 years), baseline care status, baseline ART regimen, and viral suppression status. We anticipate that some of these subgroups will have limited participants per clinic, precluding use of Two-Stage TMLE. Therefore, we will conduct all subgroup analyses using the Single-Stage TMLE, described above. Again, all analyses will account for clustering.

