2.4 Predictor analyses

In addition to the previously described subgroup analyses, we will conduct the following analyses to elucidate outcome predictors. As outcomes, we will consider being classified as a “failure” (i.e., viral non-suppression, dead, or otherwise missing); having viral non-suppression or dying (adjusting

for missingness), and having viral suppression (adjusting for missingness and censoring at death). Sensitivity analyses will exclude participants with missing endpoint viral loads.

Within each arm separately, we will estimate unadjusted associations and adjusted associations with these outcomes. Baseline predictors will include occupation, marital status, being a parent, drinking alcohol, and mobility. Adjusted analysis will additionally control for country, sex, age, and baseline care group. Adjusted analyses will treat each baseline predictor, in turn, as the exposure variable and the remainder as the adjustment set. All analyses will be implemented with the Single-Stage TMLE and yield associations on the relative scale (statistical analogs of the causal risk ratio).

3 Impact of the roll-out of dolutegravir

During the study follow-up, dolutegravir (DTG) was rolled out across both Kenya and Uganda. According to Ministry of Health guidelines, participants with a recent (within 6 month) viral load <1000 cps/mL were eligible to switch to DTG; however, concerns of neural tube defects may have led to delays in switching for women of reproductive age, who represent the majority of our study population. Additionally, DTG is known to be more robust at achieving viral suppression than prior ART regimens. Therefore, we plan to conduct the following analyses to understand the impact of the DTG rollout on study results.

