3.1 Other potential mediators

Other potential effect mediators include

- switches to second-line therapy
- engagement in care, defined as having any clinic contact in the 6 months preceding the endpoint window
- postpartum status, defined as in two ways: (i) reporting a birth within 6 months of the endpoint viral load measurement, and (ii) reporting a birth within 12 months of the endpoint viral load measurement

To understand the impact of these post-baseline events on viral suppression and other secondary endpoints (described below), we may conduct analogous analyses as for the switch to DTG.

4 Secondary health endpoints

We will evaluate the SEARCH-Youth intervention effect on the following secondary endpoints. For each secondary endpoint (unless noted), a Single-Stage TMLE will be used to evaluate the intervention effect. We will use the same approach to define the primary and secondary analytic populations as for the primary endpoint (viral suppression at 2 years). We will also use the same approach to covariate adjustment, consider the same subgroups, and may implement analogous predictor analyses.

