7.2 Power calculations

Sample size and power calculations were based on the standard formulas for cluster randomized trials with proportion endpoints [11]. We expect these calculations to be conservative, because of the precision gained through covariate adjustment in the analysis as well as our pre-specified choice of a one-sided hypothesis test.

We estimated 28 clinics (14 clinics/arm) would provide 80% power to detect at least a 24% relative increase in viral suppression at 2 years (the primary outcome) from 65% in the standard-of-care, using a two-sided test and assuming a coefficient of variation of $k=0.175$ and at least 50 participants/clinic. As shown in the following Figure, these calculations are fairly insensitive to the number of participants. Under weaker clustering ($k=0.125$) or higher viral suppression in the standard-of-care arm, we anticipate being powered to detect smaller effects.

References

- [1] M. van der Laan and S. Rose. *Targeted Learning: Causal Inference for Observational and Experimental Data*. Springer, New York Dordrecht Heidelberg London, 2011.
- [2] L.B. Balzer, M. van der Laan, J. Ayieko, M. Kamya, et al. Two-stage TMLE to reduce bias and improve efficiency in cluster randomized trials. Technical report, arXiv: <https://arxiv.org/abs/2106.15737>, 2021. URL <https://arxiv.org/abs/2106.15737>.
- [3] M.J. van der Laan, E.C. Polley, and A.E. Hubbard. Super learner. *Statistical Applications in Genetics and Molecular Biology*, 6(1):25, 2007. doi: 10.2202/1544-6115.1309.
- [4] L. Balzer, M. van der Laan, M. Petersen, and the SEARCH Collaboration. Adaptive pre-specification in randomized trials with and without pair-matching. *Statistics in Medicine*, 35(10):4528–4545, 2016. doi: 10.1002/sim.7023.
- [5] A. Benitez, M.L. Petersen, M. van der Laan, N. Santos, E. Butrick, D. Walker, R. Ghosh, P. Otieno, P. Waiswa, and L.B. Balzer. Comparative methods for the analysis of cluster randomized trials. <https://arxiv.org/abs/2110.09633>, 2021.
- [6] J. Neyman. Sur les applications de la theorie des probabilités aux expériences agricoles: Essai des principes (In Polish). English translation by D.M. Dabrowska and T.P. Speed (1990). *Statistical Science*, 5:465–480, 1923.
- [7] D.B. Rubin. Comment: Neyman (1923) and causal inference in experiments and observational studies. *Statistical Science*, 5(4):472–480, 1990.

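### The SAP fixes 26 degrees of freedom for every analysis, but country subgroups and within-arm predictor analyses rest on 14 clinics and support only 12 or 13

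*SAP*

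**What the plan says.** SAP section 2, in its paragraph on statistical inference, bases standard errors on the influence curve. For all analyses it takes the t-distribution with 28−2 = 26 "degrees of freedom as finite sample approximation to the standard normal distribution". The form is clinics minus 2, but it is written as a constant. SAP 2.1 refers the Single-Stage TMLE back to the same clustered inference, and neither document gives another value.

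Three sets of analyses use fewer than 28 clinics:

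- **Country subgroups.** SAP 2.2 lists "pre-specified baseline subgroups: country, sex, age group" and further factors, and states that "we will conduct all subgroup analyses using the Single-Stage TMLE, described above". SAP 1.1 gives the clinic count: "a total of 28 clinics (14 per country) were randomized to the SEARCH-Youth intervention". SAP section 4 extends this to the secondary endpoints: "We will also use the same approach to covariate adjustment, consider the same subgroups".
- **Predictor analyses.** SAP 2.4: "Within each arm separately, we will estimate unadjusted associations and adjusted associations". Each arm has 14 clinics (SAP 7.2: "We estimated 28 clinics (14 clinics/arm) would provide 80% power").
- **Optional exclusion analysis.** SAP 2.1 allows a sensitivity analysis that leaves out clinics with existing adherence and retention programs. It does not say how many there are.

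**The concern.** The SAP uses t rather than the normal distribution because the number of independent units is small. That correction matters most where clinics are fewest, and there the constant 26 understates it. Code written to the SAP would apply 26 to a 14-clinic analysis, and departing from it later would be an unplanned change.

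At stake are the country-specific intervals and one-sided tests, for the primary endpoint and the secondary endpoints, and the within-arm predictor intervals. All would tend to look somewhat more precise than 14 clinics allow.

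**Working it through.** **Inputs.** 28 clinics in all, 14 per country (SAP 1.1); 14 per arm (SAP 7.2); arms balanced within country, so about 7 against 7 (Protocol 4.1); one-sided tests at 5% and two-sided 95% intervals (SAP section 2).

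**The plan's own figure.** Clinics minus 2 = 28 − 2 = 26. This reproduces and is correct for the 28-clinic primary effect.

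**The same rule on 14 clinics.** A country subgroup compares two arms: 14 − 2 = 12. A within-arm predictor analysis has no arm contrast, and the SAP states no single-arm rule. Clinics minus 1 gives 13 and clinics minus 2 gives 12; neither is near 26.

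**Critical values.**

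| df | one-sided 5% | two-sided 5% | interval width relative to 26 df |
|---|---|---|---|
| 26 | 1.706 | 2.056 | 1.000 |
| 13 | 1.771 | 2.160 | 1.051 |
| 12 | 1.782 | 2.179 | 1.060 |

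Using 26 makes the two-sided value too small by 1 − 2.0555/2.1788 = 5.7% against 12 df, and by 1 − 2.0555/2.1604 = 4.9% against 13 df.

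**Effect on a simple t contrast of equally weighted clinic means.**

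- Against 12 df: coverage = 1 − P(|T12| > 2.0555) = 1 − 0.0623 = 93.8%; one-sided error = P(T12 > 1.7056) = 5.7%.
- Against 13 df: coverage = 1 − 0.0605 = 94.0%; one-sided error = 5.6%.

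**Check with an estimator nearer the plan's.** The Single-Stage TMLE "thus weights participants, not clinics, equally", so the simple contrast is only an approximation to it. I simulated an unadjusted participant-weighted log risk ratio with a clinic-aggregated influence-curve variance (divisor clinics minus 1). The set-up was 7 against 7 clinics, 50 to 100 participants each, the SAP's 65% and k = 0.175, strata unrelated to outcome, and 60,000 null replicates. Coverage was about 92.8% with 26 df and about 94.1% with 12 df. Changing the degrees of freedom therefore recovers about 1.3 points. The rest of the shortfall comes from the variance estimator: with divisor clinics minus 2, coverage was 93.8% and 95.1%.

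**Exclusion analysis.** The number of clinics left is not given. If it were 24, 20 or 16 (assumed), the rule gives 22, 18 or 14 df, and intervals based on 26 would be 0.9%, 2.2% or 4.2% too narrow.

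**The case against.** The strongest case against has three parts.

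**The effect is small and nothing confirmatory depends on it.** This stands. The loss is a little over one point of coverage, in subgroup, predictor and optional analyses.

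**Stratified randomisation may offset it in the country subgroups.** SAP 1.1 stratifies on country, clinic size and earlier SEARCH participation in order to gain power, which presumes that these factors predict outcome. If they do and are not adjusted for, the influence-curve variance is too large and works against the small critical value. In the simulation above, suppose clinic size and earlier participation each explain 5% of the between-clinic variance (assumed). Coverage is then about 94 to 95% with 26 df and 95 to 96% with 12, so neither is clearly closer to nominal. At 10% each it is about 95 to 96% with 26 and about 97% with 12. This also stands: the direction of the net error in the country subgroups is not established. But the documents do not say how prognostic the strata are, so the plan cannot rely on the offset. It does not reach the predictor analyses, which are not randomised contrasts.

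**The choice between 12 and 13 within one arm is a judgement.** True, since the SAP has no single-arm rule. Both values rest on 14 clinics, and 26 does not.

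A reader might also infer that every subgroup is affected. The documents do not support that. Sex and age groups, for example, can draw on all 28 clinics. Country is the one listed subgroup that must halve the number of clinics.

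**Conclusion.** The constant is wrong as written for analyses that use a subset of clinics. The critical value is about 5 to 6% too small for the country subgroups and the within-arm predictor analyses, and too small by an unknown, probably lesser, amount for the exclusion analysis. The figures of 93.8% coverage and 5.7% one-sided error (94.0% and 5.6% against 13 df) assume a simple t contrast on 14 clinics with strata unrelated to outcome.

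Two stronger readings are tempting. One is that the trial's main conclusion is at risk; it is not, because all 28 clinics enter the primary effect and 26 is right there. The other is that the country results are certain to be anti-conservative, or that the whole simulated shortfall, to 92.8%, is due to the degrees of freedom. The first part depends on how prognostic the strata are, which the documents do not say, and part of the shortfall comes from the variance estimator. What remains is a modest error in secondary results that costs little to correct.

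**What to change.** In the statistical inference paragraph of SAP section 2, replace the constant with a rule: *the number of clinics contributing to the analysis minus 2, less the number of any clinic-level stratum terms fitted*. This leaves 26 for the primary effect, gives 12 for each country, and adjusts itself in the exclusion analysis once the number of remaining clinics is known. In SAP 2.4, state that within-arm predictor analyses use clinics minus 1, that is 13.

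The cost is one or two sentences in the SAP and one argument in the code. Country intervals become 6.0% wider (2.179/2.056) and predictor intervals 5.1% wider (2.160/2.056). If the within-country strata are prognostic and not adjusted for, the 12-df country intervals may be somewhat conservative. Stratum terms need not be fitted in the country subgroups. If they are, one term gives 11 df (7.1% wider than with 26) and two give 10 df (8.4% wider). The primary analysis does not change.

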2.1 Sensitivity analyses

In addition to the previously described sensitivity analyses, we will evaluate the intervention effect using a *Single-Stage TMLE* that pools across clinics to estimate and compare the average of individual-level outcomes between arms [2, 5, 12]. This approach naturally estimates an individual-level effect (e.g., the by-arm contrast in the overall proportion with viral suppression) and thus weights participants, not clinics, equally. As detailed in [5], however, this effect can equivalently be estimated with Two-Stage TMLE when the appropriate weights are applied. The single-stage approach is preferable when the cluster size is small or the outcome is rare. (The two-stage approach is preferable when the outcome is subject to differential measurement or censoring.)

In sensitivity analyses of the primary endpoint evaluated with the Single-Stage TMLE, we will adaptively select from the following prespecified set the combination of baseline variables that maximizes empirical efficiency: age, sex, viral suppression status, or nothing (unadjusted). In sensitivity analyses of secondary endpoints adjusting for potentially differential measurement of viral loads, we will include these variables as well as the post-baseline variable of outmigration in the adjustment set in a longitudinal TMLE [13, 14]. Throughout statistical inference will account for clustering through influence curve-based estimation, described above.

As an additional sensitivity analysis, we may define viral suppression as HIV RNA<50 cps/mL.

Finally, given existing programs to support adherence and retention among adolescents and young adults with HIV in study clinics, we may conduct sensitivity analyses to exclude these clinics. We

note both intervention and control participants had full access to these programs; the intervention was added to, not in place of, the standard-of-care.

2.2 Subgroups

To understand effect heterogeneity, we will repeat the above analyses within the following pre-specified baseline subgroups: country, sex, age group (15-19 years; 20-24 years), baseline care status, baseline ART regimen, and viral suppression status. We anticipate that some of these subgroups will have limited participants per clinic, precluding use of Two-Stage TMLE. Therefore, we will conduct all subgroup analyses using the Single-Stage TMLE, described above. Again, all analyses will account for clustering.

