9.4.2 ANALYSIS OF THE PRIMARY ENDPOINT(S)

Primary Outcome: Proportion of study participants with virologic suppression (HIV RNA <400 c/mL) at 2 years of follow-up

Primary Predictor: Clinic Randomized Arm (intent-to-treat), Intervention or Control.

Analytic Plan: The primary analysis of the full RCT will be an adjusted comparison of the proportion of AYAH with HIV virologic suppression (HIV-1 RNA copies <400 c/mL,) measured at 2 years on study between those enrolled at clinics randomized to the intervention condition (n=14 clinics) versus those enrolled at clinics randomized to the control condition (n=14 clinics). The primary analysis will restrict to participants enrolled prior to December 1, 2019; secondary analyses will include all participants. Viral suppression will be compared between arms using Two-Stage TMLE, an approach that appropriately accounts for the dependence of outcomes within clinics. In the first stage, viral suppression will be estimated for each clinic, using TMLE to adjust for possibly incomplete ascertainment of viral loads. In the second stage will use a cluster-level TMLE to estimate intervention effectiveness by comparing the clinic-specific endpoints between randomized arms, while accounting for the randomization scheme. We will test the null hypothesis that the intervention did not impact viral suppression with a two-sided test at the 5% significance level. To understand effect heterogeneity, we will repeat these analyses within the following pre-specified subgroups: country, baseline care status, baseline viral suppression status, gender, age group, and pregnancy or live birth during the study (among women).

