We will test the *null hypothesis* that the SEARCH-Youth intervention did not improve viral suppression, as compared to the optimized standard-of-care, with a one-sided test at the 5% significance level. We will report point estimates and two-sided 95% confidence intervals for the arm-specific endpoints as well as the relative and absolute effects.

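### SAP 2.2 sets out to examine effect heterogeneity across six baseline factors but never estimates or tests the difference between levels of any factor

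*SAP*

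**What the plan says.** SAP 2.2 gives its purpose and its method in one sentence: "To understand effect heterogeneity, we will repeat the above analyses within the following pre-specified baseline subgroups". The factors are "country, sex, age group (15-19 years; 20-24 years), baseline care status, baseline ART regimen, and viral suppression status". On the estimator it says "we will conduct all subgroup analyses using the Single-Stage TMLE, described above", with clustering accounted for.

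The analyses being repeated are those of SAP Section 2. They test whether the intervention improved suppression "with a one-sided test at the 5% significance level", and they also report intervals: "We will report point estimates and two-sided 95% confidence intervals for the arm-specific endpoints as well as the relative and absolute effects". SAP Section 4 carries the scheme to the secondary endpoints, for which the team will "consider the same subgroups, and may implement analogous predictor analyses".

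Protocol 9.4.2 takes the same approach ("To understand effect heterogeneity, we will repeat these analyses within the following pre-specified subgroups"), but its test is "with a two-sided test at the 5% significance level" and its list has pregnancy or live birth where the SAP has baseline ART regimen. Protocol 9.4.7 lists subgroups and adds no contrast.

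The only mention of moderation is in Protocol 9.4.3.1. There sex, age and region are moderators inside the mediation models for intervention components. The SAP does not take this up.

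**The concern.** Heterogeneity is a statement about the difference between two subgroup effects. The plan produces each subgroup effect separately and stops there. Neither document names an interaction contrast or a ratio of risk ratios, and neither gives a rule for interpreting the set of level-specific results.

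A significant result in one level and a non-significant one in another does not show that the effects differ. Each level holds only part of the data, so a uniform effect will often reach significance in one level and miss it in the other. What is at stake is any statement about which young people benefit. The primary conclusion is not at stake.

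Separate intervals do not fully close the gap. Countries have disjoint clinics, so a reader could roughly combine the two country intervals. For sex, age, care status, regimen and baseline suppression the levels share clinics. The contrast then needs the covariance of the two estimates, which only the trial team can compute.

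**Working it through.** **Inputs.** From SAP 7.2: control suppression p0 = 0.65; relative increase 24%, so p1 = 0.65 × 1.24 = 0.806; k = 0.175, or 0.125 under weaker clustering; at least 50 participants per clinic; 14 clinics per arm. From SAP 1.1: 14 clinics per country. Protocol 4.1 says allocation is balanced within country, so I take 7 clinics per arm per country. The Protocol's 2,000 participants over 28 clinics give about 71 per clinic; I use m = 50, 71 and 100.

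**The plan's own figure.** Per-clinic variance, summed over arms:

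V = p0(1−p0)/m + p1(1−p1)/m + k²(p0² + p1²)

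At m = 50 and k = 0.175, V = 0.00455 + 0.00313 + 0.03283 = 0.04051. Clinics per arm for 80% power, two-sided 5%: 1 + (1.96 + 0.8416)² × 0.04051/0.156² = 14.07. With 14 clinics, power is 79.8%. The SAP's 80% reproduces.

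**Country, identical true effect in both.** The noncentrality is 0.156/√(V/7), with a noncentral t on 12 df and one-sided 5%. If each country has power P, exactly one is significant with probability 2P(1−P).

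| k | m | Power per country | Exactly one significant |
|---|---|---|---|
| 0.175 | 50 | 0.613 | 0.474 |
| 0.175 | 71 | 0.635 | 0.464 |
| 0.175 | 100 | 0.651 | 0.455 |
| 0.125 | 50 | 0.800 | 0.320 |
| 0.125 | 71 | 0.833 | 0.278 |
| 0.125 | 100 | 0.856 | 0.246 |

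At m = 50 and k = 0.175, both countries are significant in 38% of trials and neither in 15%. The Protocol's two-sided test does not help: power per country is then 0.471 and a split occurs with probability 2 × 0.471 × 0.529 = 0.498.

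**Two-level factor within clinics, assumed 50:50.** Each level has m/2 per clinic, so the binomial part of V doubles and the clinic part C = k²(p0² + p1²) stays. Let r be the assumed correlation of clinic effects between levels (1.0 or 0.5). The two estimates then correlate at r × C divided by the level's variance. At m = 50 and k = 0.175 the level's variance is 0.01536 + 0.03283 = 0.04819, the expected z is 0.156/√(0.04819/14) = 2.66, and the correlation is 0.68 (r = 1) or 0.34 (r = 0.5). A bivariate normal with the one-sided t cut-off on 26 df gives split verdicts in 16% and 23% of trials. At m = 100 these are about 10% and 17%. At k = 0.125 the range is 3-10%.

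**Simulation check.** Clinic-level t-tests, k = 0.175, 50 per clinic, no true heterogeneity, 10,000-20,000 runs per setting:

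- Country: split verdicts in 47% of trials at a uniform risk ratio of 1.24, 45% at 1.15, 34% at 1.10 and 10% at 1.00.
- Within-clinic factor, splits of 50:50 to 80:20, r from 0.5 to 1.0: 17-31% at 1.24 and 24-42% at 1.10-1.15.
- Direct between-level test at two-sided 5%: flags heterogeneity in 4.5-5.4% of trials in every setting.

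**Power of a direct contrast.** Suppose one country has risk ratio 1.24 and the other 1.00, with k = 0.175 and m = 50. Var(log RR) per country = [(0.35/0.65)/50 + (0.194/0.806)/50 + 2 × 0.0306]/7 = 0.0110. The SE of the log ratio is √(2 × 0.0110) = 0.148. Then log 1.24 = 0.215, 0.215/0.148 = 1.45, and power = Φ(1.45 − 1.96), about 31%. Using 65% in both arms for the null country raises the SE to 0.151 and gives about 30%.

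**The case against.** The strongest reply is that the SAP states no rule under which a split in significance means heterogeneity. A reader might infer that heterogeneity will be judged by comparing p-values, and that the results will decide where the intervention is rolled out. The documents support neither inference. Estimates and two-sided intervals accompany every test. The one-sided test within subgroups is itself inferred from the instruction to repeat the analyses, and the Protocol's version is two-sided. The only stated use of the subgroups is to understand heterogeneity. This limits the point to what can be misread.

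The Protocol's moderation analysis is partial cover for three of the six factors. It concerns mediation pathways, and it omits care status, ART regimen and baseline suppression.

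The sizes come from unadjusted clinic-level tests, whereas the subgroups use Single-Stage TMLE with adaptive adjustment, and SAP 7.2 expects adjustment to add precision. If adjustment cut variance by 20-40% (an assumption), the country figure would fall to about 28-42% at k = 0.175 and 6-22% at k = 0.125. That weakens the magnitude and leaves the missing contrast untouched.

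Low interaction power is also a fair objection. It argues for showing the contrast with its interval, because paired verdicts hide that uncertainty.

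**Conclusion.** The point holds as a gap in a supportive analysis and should be fixed. Neither SAP 2.2, SAP 4, Protocol 9.4.2 nor Protocol 9.4.7 estimates or tests a difference between levels, so the stated aim has no matching analysis.

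With a truly uniform effect at the SAP's design values, a split verdict between countries is expected in about 45-47% of trials (25-32% at k = 0.125), and in about 10-23% for an even within-clinic split (3-10% at k = 0.125). Uneven splits or smaller effects raise the within-clinic figures. A direct contrast would mislead about 5% of the time.

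These figures assume 7 clinics per arm per country, unadjusted clinic-level tests as a stand-in for the TMLE, and, within clinics, the split and correlations stated. They show how easily results could be misread. They do not predict that the team will misread them, and they do not touch the primary estimate, test or error rate.

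**What to change.** Add to SAP 2.2, and by reference to SAP 4:

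- For each factor, an exploratory between-level contrast: the ratio of subgroup risk ratios with two-sided 95% interval and p-value, from influence curves aggregated by clinic so that shared clinics are accounted for.
- A joint test for factors with three or more levels, such as care status (three levels in SAP 1.2). State the ART regimen levels, which SAP 2.2 does not give.
- Heterogeneity statements rest on this contrast and its interval, not on level-by-level significance. Level-specific effects continue to be shown with their intervals.
- State the number of contrasts and that they are not adjusted for multiplicity. Six tests at 5% carry up to about 1 − 0.95⁶ = 26% chance of at least one false positive per endpoint, treating them as independent.
- State that a non-significant contrast does not show homogeneity.
- Reconcile the one-sided (SAP) and two-sided (Protocol) tests for the level-specific analyses.

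The cost is a few sentences and one further contrast per factor, from quantities the Single-Stage TMLE already produces. No new data are needed. The real downside is low power, so most contrasts will be inconclusive and should be reported as such.
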